***This will be explicitly asked and documented in the EMR by treating radiation oncologist**
 - 3.2.8.1 Dental operations do not include routine cleaning or cavity fillings
 - 3.2.8.2 Dental operations that exclude patients refer to any manipulation of mandible.
- 3.2.9 Positive urine pregnancy test in women of child bearing potential within 1 week of registration. Pregnant women are excluded from this study because radiation has clear teratogenic and potentially abortifacient risks.

3.3 Inclusion of Women and Minorities

Men and women of all races and ethnicities who meet the above-described eligibility criteria are eligible to participate in this study. The study consent form will also be provided in Spanish for Spanish-speaking participants.

Based on WFBCCC population estimates, we may expect approximately 44% of participants to be women. Translating this to our sample size estimate of 84 patients, we may enroll approximately 42 women. We may enroll approximately 10-13% Black or African American patients. Based on our catchment area and hospital demographics we do not expect high accruals of individuals of Hispanic/ Latino, American Indian/Alaska Native or Asian ancestry; however, no individual will be excluded from the study if they satisfy the above inclusion/exclusion criteria. Should we not meet or exceed these estimates, the PI will engage the Office of Cancer Health Equity to discuss strategies to enhance recruitment in these target populations.

4.0 Registration Procedures

All patients entered on any WFBCCC trial, whether treatment, companion, or cancer control trial, **must** be linked to the study in EPIC within 24 hours of Informed Consent. Patients **must** be registered prior to the initiation of treatment. You must perform the following steps in order to ensure prompt registration of your patient:

- 1.0 Complete the Eligibility Checklist (Appendix A)
- 2.0 Complete the Protocol Registration Form (Appendix B)
- 3.0 Alert the Cancer Center registrar by phone, *and then* send the signed Informed Consent Form, Eligibility Checklist and Protocol Registration Form to the registrar, either by fax or e-mail.

Contact Information:

Protocol Registrar [contact]
Protocol Registrar [contact]
Protocol Registrar E-MAIL ([contact])

*Protocol Registration is open from 8:30 AM - 4:00 PM, Monday-Friday.

4.0 Fax/e-mail ALL eligibility source documents with registration. Patients **will not** be registered without all required supporting documents.

Note: If labs were performed at an outside institution, provide a printout of the results.
Ensure that the most recent lab values are sent.

To complete the registration process, the Registrar will:

- assign a patient study number
- randomize the patient
- other appropriate actions
- register the patient on the study

5.0 Study Outcomes and Study Measures

All CT imaging referenced below is performed as a routine standard of care and necessary for cancer treatment follow-up. These chest CT scans utilized in this research protocol would be performed every 3 months regardless of inclusion on this trial.

5.1 Primary Outcome

- 5.1.1 The primary outcome measure is the percent change in mean cortical thickness (C.Th) of bones receiving 30 Gy or more at 3 months post SBRT, when compared to pre-SBRT cortical thickness

5.2 Secondary Outcomes

- 5.2.1 The change in mean C.Th of bones will be assessed in regions of bone that received 0 – 10 Gy, >10 – 20 Gy, > 20 – 30 Gy, > 30 – 40 Gy, and > 40 Gy at all time points including 3 months, 6 months, 9 months, and 12 months.
- 5.2.2 Chest wall pain incidence and grade will be collected as per modified CTCAE v. 5 within the within the 50% isodose line. Appendix K
- 5.2.3 Incidence of rib and vertebral fractures (as noted on CT imaging) that occur within 12 months of irradiation and are within the within 50% isodose line.
- 5.2.4 The urine concentration of an osteoclast-specific biomarker, urinary N-telopeptide (U-NTX) indicating osteoclastic activity will be assessed prior to SBRT and at each routine follow up visit (at 3 months, 6 months, 9 months, and 12 months post SBRT).

5.3 Exploratory Outcomes

- 5.3.1 We will contour the neurovascular bundle that runs in the intercostal space for each patient within at least 3 cm of the planning tumor volume. We will then utilize stored treatment planning information and the raystation planning system to calculate the dose that this nerve bundle received at the time of treatment. As patients have already been assessed for development of chest wall pain at each follow up, we will assess for a dose response relationship between the dose to the nerve bundle and the subsequent development of and grade of any chest wall pain per the CTCAE v5.
- 5.3.2 Urine concentrations (pg/mL) of markers of bone turnover activity such as P1NP (procollagen type 1 pro-peptide), sclerostin, OPG (osteoprotegerin), TRAP5B, and pentosidine (an advanced glycation end-product (AGE)); will be analyzed using ELISAs. These markers will be assessed prior to SBRT and at the 6 month follow up visit post SBRT).
- 5.3.3 Urine concentrations (pg/mL) of pain-associated cytokines derived from the Isoplexis Codeplex Secretome Human Adaptive Immune and Innate Immune Chips which include GM-CSF, IL-1 β , IL-7, IL-17A, TNF- α , PDGF-BB, and VEGF will be assessed prior to SBRT and at the 6 month follow up visit post SBRT. In addition, other pro-inflammatory cytokines may be measured and analyzed on these chips as available. Also, if funding permits, the urine concentration (pg/mL) of pain-related neurotrophic growth factors (proNGF, proBDNF, GDNF) and neuropeptides (CGRP and Substance P) will be measured by ELISA.

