7.4 Urine Biomarkers of Osteoclastic Activity and Bone Turnover

A single urine sample will be collected at baseline and at each follow up point (3,6,9,12 months). Samples will be collected in clinic and immediately transported to the laboratory of [name] on campus for storage in an minus 80 degrees C freezer designed for lab specimen storage. Urinary N-telopeptide (U-NTX) will be measured using ELISA based on an immobilized synthetic peptide with a specific sequence of amino acids matching a section of the N telopeptide (NTX) of type 1 collagen. Samples will be destroyed in biohazard waste immediately after analysis is complete.

The following detailed information on collection and analysis is provided from pacific biomarkers
<https://pacbio.com/ biomarker/assay-detail/148/>

Specimen Type: Urine (2nd morning void preferred; do not add preservative)

Optimum Volume: 1 mL

Stability:

2-8°C	-20°C	-70°C
1 week	3 months	1 year

Reporting units: nM BCE/mmol Cr (normalized)

Method: ELISA

Biological or Clinical Significance:

Bone resorption is a function of osteoclasts. These cells remove the mineral from bone and break down the organic matrix that is primarily comprised of type I collagen. Collagen is a cross-linked fibrous protein that forms the fabric of bone and most other connective tissues. Bone contains three polypeptide chains wound together in a helical structure. The ends of these chains (known as telopeptides) provide the intermolecular cross-linking that gives collagen its strength and resiliency. As these cross-linked domains from bone and other skeletal connective tissues are broken down, the pyridinoline cross-linking domains are released and ultimately excreted into the urine in the form of small peptides bound to pyridinoline (70%) and free pyridinoline (30%). One type of peptide-bound pyridinoline is the cross-linked N-telopeptide (NTX) which is unique to type I bone collagen. NTX can be used to identify fast losers of bone, to monitor therapy, to measure dose response, or to determine patient compliance with therapeutic prescription(s).

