A growing body of clinical studies has shown that urinary NTx provides a sensitive marker of human bone resorption. Its specificity is based on originating solely from type I collagen, being particularly enriched as a cross-linking structure in bone type I collagen and being produced directly as a proteolytic neoepitope by osteoclast activity during bone resorption. Analysis of urine specimens has certain advantages, including ease of collection and reduced biohazard precautions for clinical laboratory personnel than with bloodbased specimens. However, the obtained results need to be normalized to creatinine.

Principle of Test Method:

The NTX assay is a competitive, enzyme-linked immunosorbent assay (ELISA) for the quantitative measurement of the NTX in human urine. NTX is reported as a normalized ratio to urinary creatinine in order to account for variations in urine flow rate. Therefore NTX and urine creatinine are preferably tested from the same aliquot.

7.5 Evaluable for toxicity:

All patients will be evaluable for toxicity from the time of their first treatment with risedronate, which will be given prior to start of SBRT

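### The exploratory urine markers are specified in pg/mL with no dilution correction, although NTX from the same collections is normalised to creatinine; this may cost precision in the group-by-time tests

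*Combined protocol and SAP*

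**What the plan says.** Section 5.3.2 lists "Urine concentrations (pg/mL) of markers of bone turnover activity such as P1NP" and others, and 5.3.3 lists "Urine concentrations (pg/mL) of pain-associated cytokines". For the optional assays, 5.3.3 adds "the urine concentration (pg/mL) of pain-related neurotrophic growth factors" together with neuropeptides. All are measured before SBRT and at the 6-month visit. Sections 11.3.2 and 11.3.3 plan repeated measures analyses (for the bone markers, one model per marker) and look for a group-by-time interaction. Neither section names a creatinine ratio, a creatinine covariate or a transformation.

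Section 7.4 provides for one urine sample per visit, with a second morning void preferred but not required. It gives the NTX unit per mmol of creatinine and explains: "NTX is reported as a normalized ratio to urinary creatinine in order to account for variations in urine flow rate". In the same assay description, after discussing the use of urine specimens, it says that "the obtained results need to be normalized to creatinine".

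**The concern.** A concentration per mL of a single void reflects both how much marker is excreted and how dilute the urine is. Section 7.4 recognises this for NTX and corrects for it. The exploratory markers come from the same collections, and the collection rules do not control dilution, yet their stated unit contains no correction.

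With only two visits, the group-by-time test compares within-patient change between arms. Independent variation in dilution at each visit goes straight into the variance of that change. At stake is the precision of the exploratory comparisons: a real effect on a marker could be missed because of noise that the trial already has the means to reduce.

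**Working it through.** **1. The plan's own sample size.** Section 11.4 gives 42 per group for cortical thickness: difference in mean change 0.22 − 0.11 = 0.11 mm, SD 0.20 mm, power 0.80, one-sided alpha 0.05.

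- Normal approximation: n = 2 × (1.645 + 0.842)² × (0.20/0.11)² = 40.9, so 41 per group.
- With the noncentral t distribution: 42 per group.

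The stated figure reproduces. It concerns the primary outcome only. No sample size or power is claimed for the urine markers, and 42 per group is used below only as a convenient size.

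**2. Effect of dilution on the interaction test.** Work on the log scale. Let s_w be the within-patient SD of the marker and s_d the SD of dilution at a visit, independent between visits. With two visits:

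- variance of change without dilution noise = 2 s_w²
- variance of change with dilution noise = 2 (s_w² + s_d²)
- ratio = 1 + R², where R = s_d / s_w

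Take an effect that would have 80% power without dilution noise (two-sided 0.05, 42 per group). Its power with dilution noise is Φ[(1.960 + 0.842)/√(1 + R²) − 1.960]. The number per group needed to regain 80% is 42 × (1 + R²), rounded up.

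The documents give neither SD, so R is an assumption and is shown over a range:

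| R | 1 + R² | Power | n per group for 80% |
|---|---|---|---|
| 0.25 | 1.06 | 78% | 45 |
| 0.5 | 1.25 | 71% | 53 |
| 0.75 | 1.56 | 61% | 66 |
| 1 | 2.00 | 51% | 84 |
| 1.5 | 3.25 | 34% | 137 |
| 2 | 5.00 | 24% | 210 |

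**3. Two examples with assumed coefficients of variation.** Use log-scale SD = √ln(1 + CV²).

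- Dilution CV 50%, marker CV 60%: s_d = √ln 1.25 = 0.47, s_w = √ln 1.36 = 0.55, R = 0.85. Dilution is 42% of the change variance and power is 57%. The fold change detectable with 80% power rises from 1.62 to 1.88.
- Dilution CV 30%, marker CV 100%: s_d = √ln 1.09 = 0.29, s_w = √ln 2 = 0.83, R = 0.35. Dilution is 11% of the variance and power is 75%.

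**4. Type I error.** In 20,000 simulated trials under the null (42 per arm, raw scale, dilution CV 50% and marker CV 60% in both arms), the two-sample test of change scores rejected in 5.0% at a nominal 5%. Dilution noise that is equal in both arms costs power and does not create false positives.

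**The case against.** The strongest reply is that pg/mL is simply what the assays deliver. Section 5.3 gives the unit beside the assay platform, while 11.3 states no analysis scale. Sections 2.2.4, 5.2.4 and 11.2.4 also call NTX a concentration, although 7.4 normalises it. This has some force: the plan nowhere says outright that uncorrected values will be modelled. But the NTX outcome sections give no unit and 7.4 supplies a normalised one. For the exploratory markers the only unit given is pg/mL, which cannot be a creatinine ratio, and nothing later changes it.

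Three stronger readings are tempting, and the documents do not support them:

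- **That the protocol requires all urine results to be normalised.** The sentence stands in assay text taken from the laboratory vendor and concerns NTX. Its reason, urine flow, carries over to other analytes. The rule itself is not stated for them.
- **That dilution will dominate the test.** It exceeds half of the change variance only if R is above 1, and the documents give no basis for R.
- **That a shift in hydration or renal function would mimic a treatment effect.** In a randomised, double-blind comparison, a shift common to both arms belongs to the time effect and, on the log scale, cancels from the interaction. Only a shift that differs between arms could bias the test, and nothing in the documents points to one. A common shift could still mislead a reading of change within one arm.

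It is also fair to say that the consequence is limited. These outcomes are exploratory, no power is claimed, and 2.3.2 and 2.3.3 make the bone markers, growth factors and neuropeptides depend on funding. Correction could be added at analysis, but choosing the scale for many markers after seeing the results invites selective reporting.

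**Conclusion.** The point holds as an inconsistency of low severity. The plan corrects NTX for urine dilution and, as written, does not correct the other analytes from the same collections, although its reason for correcting applies to them too. The expected harm is reduced precision of the exploratory group-by-time tests.

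The inconsistency is clear from the text. The amount of precision lost is not known. Over the assumed range, 80% power becomes anything from 78% (R = 0.25) to 24% (R = 2). These figures rest on log-scale change scores, dilution independent between visits, and creatinine correction that removes all dilution noise and adds none, so for a given R they are upper bounds on the gain. They also take 42 per group at 6 months. Section 6.4 withdraws patients who need further chemotherapy, so fewer may contribute.

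**What to change.** In 5.3.2, 5.3.3, 11.3.2 and 11.3.3, state that each exploratory marker is analysed as log(marker/urine creatinine), or as log marker with log urine creatinine as a covariate. The covariate form lets the data set the strength of the correction. Name one of the two before unblinding, and keep raw pg/mL as a supporting display.

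Use the creatinine from the same visit's sample at baseline and 6 months, which NTX reporting already requires. Record it as a value of its own and not only inside the NTX ratio. Link it to the exploratory results, because the data management table in section 10.0 lists the urine bone-turnover form under OnCore and the exploratory markers under REDCap.

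The cost is a change of wording and one data link. No new visit, sample or assay is needed.

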6.0 Treatment Plan

6.1 Treatment Administration

Treatment will be administered on an outpatient basis.

Reported adverse events and potential risks of SBRT and risedronate are described in Section 8.

REGIMENT DESCRIPTION			
Agent	Dose	Route	Schedule
Risedronate	150 mg	Oral	Given once 7 – 21 days prior to initiation of SBRT
Matching Placebo	N/A	Oral	Given once 7 – 21 days prior to initiation of SBRT

Standard of care radiation therapy with SBRT will be given over the course of 3 – 10 fractions to a total dose of 50 – 60 Gy at the discretion of the treating radiation oncologist. Specific dose fractionations between 3 – 10 fractions and constraints will be at the discretion of the treating radiation oncologist and may be prescribed every day or every other day. Respecting the following constraints are encouraged but meeting these constraints is not required for inclusion in the study. In many cases meeting the rib constraint will not be possible.

Treatment planning will be performed utilizing a vac lock or body fix bag and optional abdominal compression at the discretion of the treating radiation oncologist. Planning CT chest may be performed with or without contrast at the discretion of the treating radiation oncologist. Utilization of motion management with 4D cinematic CT or a slow scan is required for determination of the internal target volume (ITV). Clinical treatment volume (CTV) creation is not necessary and is not our standard treatment paradigm with SBRT for peripheral lung tumors. The planning target volume (PTV) is generally created as a 0.5 cm expansion from the ITV, however the exact dimensions of this expansion are at the discretion of the treating radiation oncologist.

The following are encouraged but not required dose constraints.

Three Fractions

Serial Tissue	Volume	Volume Max (Gy)	Max Point Dose (Gy)	Endpoint (≥Grade 3)
Spinal Cord	<0.5 cc	18 Gy (6 Gy/fx)	22 Gy (7.33 Gy/fx)	myelitis
Cauda Equina	<5 cc	21.9 Gy (7.3 Gy/fx)	24 Gy (8 Gy/fx)	neuritis
Sacral Plexus	<3 cc	22.5 Gy (7.5 Gy/fx)	24 Gy (8 Gy/fx)	neuropathy
Esophagus*	<5 cc	21 Gy (7 Gy/fx)	27 Gy (9 Gy/fx)	stenosis/fistula
Ipsilateral Brachial Plexus	<3 cc	22.5 Gy (7.5 Gy/fx)	24 Gy (8 Gy/fx)	neuropathy
Heart/Pericardium	<15 cc	24 Gy (8 Gy/fx)	30 Gy (10 Gy/fx)	pericarditis
Great vessels	<10 cc	39 Gy (13 Gy/fx)	45 Gy (15 Gy/fx)	aneurysm
Trachea and	<4 cc	15 Gy (5 Gy/fx)	30 Gy (10 Gy/fx)	stenosis/fistula
Ipsilateral Bronchus*				
Skin	<10 cc	22.5 Gy (7.5 Gy/fx)	24 Gy (8 Gy/fx)	ulceration
Stomach	<10 cc	21 Gy (7 Gy/fx)	24 Gy (8 Gy/fx)	ulceration/fistula
Duodenum*	<5 cc	15 Gy (5 Gy/fx)	24 Gy (8 Gy/fx)	ulceration
Jejunum/Ileum*	<5 cc	16.2 Gy (5.4 Gy/fx)	27 Gy (9 cGy/fx)	enteritis/obstruction
Colon*	<20cc	20.4 Gy (6.8 Gy/fx)	30 Gy (10 Gy/fx)	colitis/fistula
Rectum*	<20cc	20.4 Gy (6.8 Gy/fx)	30 Gy (10 Gy/fx)	proctitis/fistula
Bladder wall	<20 cc	15 Gy (5 Gy/fx)	30 Gy (10 Gy/fx)	cystitis/fistula
Femoral Heads	<10 cc	21.9 Gy (7.3 Gy/fx)		necrosis
Renal hilum	<2/3 volume	18.6 Gy (6.2 Gy/fx)		malignant hypertension

Five Fractions

Serial Tissue	Volume	Volume Max (Gy)	Max Point Dose (Gy)	Endpoint (\geq Grade 3)
Spinal Cord	<0.5 cc	22.5 Gy (4.5 Gy/fx)	30 Gy (6 Gy/fx)	myelitis
Cauda Equina	<5 cc	30 Gy (6 Gy/fx)	34 Gy (6.4 Gy/fx)	neuritis
Sacral Plexus	<3 cc	30 Gy (6 Gy/fx)	32 Gy (6.4 Gy/fx)	neuropathy
Esophagus*	<5 cc	27.5 Gy (5.5 Gy/fx)	35 Gy (7 Gy/fx)	stenosis/fistula
Ipsilateral Brachial Plexus	<3 cc	30 Gy (6 Gy/fx)	32 Gy (6.4 Gy/fx)	neuropathy
Heart/Pericardium	<15 cc	32 Gy (6.4 Gy/fx)	38 Gy (7.6 Gy/fx)	pericarditis
Great vessels	<10 cc	47 Gy (9.4 Gy/fx)	53 Gy (10.6 Gy/fx)	aneurysm
Trachea and	<4 cc	18 Gy (3.6 Gy/fx)	38 Gy (7.6 Gy/fx)	stenosis/fistula
Ipsilateral Bronchus*				
Skin	<10 cc	30 Gy (6 Gy/fx)	32 Gy (6.4 Gy/fx)	ulceration
Stomach	<10 cc	28 Gy (5.6 Gy/fx)	32 Gy (6.4 Gy/fx)	ulceration/fistula
Duodenum*	<5 cc	18 Gy (3.6 Gy/fx)	32 Gy (6.4 Gy/fx)	ulceration
Jejunum/Ileum*	<5 cc	19.5 Gy (3.9 Gy/fx)	35 Gy (7 Gy/fx)	enteritis/obstruction
Colon*	<20cc	25 Gy (5 Gy/fx)	38 Gy (7.6 Gy/fx)	colitis/fistula
Rectum*	<20cc	25 Gy (5 Gy/fx)	38 Gy (7.6 Gy/fx)	proctitis/fistula
Bladder wall	<20 cc	18.3 Gy (3.65Gy/fx)	38 Gy (7.6 Gy/fx)	cystitis/fistula
Femoral Heads	<10 cc	30 Gy (6 Gy/fx)	38 Gy (7.6 Gy/fx)	necrosis
Renal hilum	<2/3 volume	23 Gy (4.6 Gy/fx)		malignant hypertension

Ten Fractions

Serial Tissue	Volume	Volume Max (Gy)	Max Point Dose (Gy)	Endpoint (\geq Grade 3)
Spinal Cord	<0.5 cc	32 Gy (3.2 Gy/fx)	36 Gy (3.6 Gy/fx)	myelitis
Cauda Equina	<5 cc	36 Gy (3.6 Gy/fx)	40 Gy (4.0 Gy/fx)	neuritis
Sacral Plexus	<3 cc	37 Gy (3.7 Gy/fx)	44 Gy (4.4 Gy/fx)	neuropathy
Esophagus*	<5 cc	40 Gy (4 Gy/fx)	50 Gy (5.0 Gy/fx)	stenosis/fistula
Ipsilateral Brachial Plexus	<3 cc	37 Gy (3.7 Gy/fx)	44 Gy (4.4 Gy/fx)	neuropathy
Heart/Pericardium	<15 cc	39 Gy (3.9 Gy/fx)	45 Gy (4.5 Gy/fx)	pericarditis
Great vessels	<10 cc	58 Gy (5.8 Gy/fx)	64 Gy (6.4 Gy/fx)	aneurysm
Trachea and	<4 cc	32 Gy (3.2 Gy/fx)	50 Gy (5.0 Gy/fx)	stenosis/fistula
Ipsilateral Bronchus*				
Skin	<10 cc	38 Gy (3.8 Gy/fx)	45 Gy (4.5 Gy/fx)	ulceration
Stomach	<10 cc	35 Gy (3.5 Gy/fx)	45 Gy (4.5 Gy/fx)	ulceration/fistula
Duodenum*	<5 cc	32 Gy (3.2 Gy/fx)	45 Gy (4.5 Gy/fx)	ulceration
Jejunum/Ileum*	<5 cc	32 Gy (3.2 Gy/fx)	45 Gy (4.5 Gy/fx)	enteritis/obstruction
Colon*	<20cc	36 Gy (3.6 Gy/fx)	50 Gy (5.0 Gy/fx)	colitis/fistula
Rectum*	<20cc	38 Gy (3.8 Gy/fx)	52 Gy (5.2 Gy/fx)	proctitis/fistula
Bladder wall	<20 cc	32 Gy (3.2 Gy/fx)	54 Gy (5.4 Gy/fx)	cystitis/fistula
Femoral Heads	<10 cc	38 Gy (3.8 Gy/fx)		necrosis
Renal hilum	<2/3 volume	35 Gy (3.5 Gy/fx)		malignant hypertension

6.2 General Concomitant Medication and Supportive Care Guidelines

Patients should receive *full supportive care*, including transfusions of blood and blood products, erythropoietin, antibiotics, antiemetics, etc., as clinically indicated. Anti-inflammatory or narcotic analgesics may be offered as needed for chest wall pain, however use of these medications must be noted. Medications considered necessary for the patient's well-being may be given at the discretion of the investigator, i.e., chronic treatments for concomitant medical conditions, as well as agents required for life-threatening medical problems, etc. The reason(s) for treatment, dosage, and dates of treatment should be recorded on the flow sheets.

6.3 Duration of Therapy

The hypothesized bone structural benefit of bisphosphonates with radiation is due to inhibition of early osteoclast activation within as little as 1 week of SBRT. In our preclinical studies, risedronate was only

given just prior to irradiation, and it was not given at all after irradiation was completed. Osteoclast activation only lasted for 1 week post irradiation in rodent models. In non-human primate models, the first follow up scans were performed at 2 months post irradiation, and these scans indicated maximal bone loss had already occurred which was persistent but not worsening on subsequent scans. For this reason, risedronate will be given only once prior to SBRT, at a dose of 150 mg, which is the recommended monthly dose in the setting of osteoporosis in post-menopausal females.

SBRT is given over the course of 3 to 10 treatments and generally this is performed over the course of 1.5 - 2 weeks. Radiation treatments are given every day or every other day Monday through Friday with the exclusion of the weekends or major holidays. In the absence of treatment delays due to adverse events, radiation treatments may continue until the planned treatment dose is reached or until one of the following criteria applies:

- Intercurrent illness that prevents further administration of treatment,
- Unacceptable adverse event(s)
- Patient decides to withdraw from the study

General or specific changes in the patient's condition render the patient unacceptable for further treatment in the judgment of the investigator.

